3.4. Secondary Safety Endpoints

1. Pressure sensor failure rate throughout the study
2. Frequency of serious adverse events throughout the study
3. Frequency of implant procedure and procedure related adverse events and serious adverse events

This document is confidential.

4. Analysis Sets

4.1. Enrolled Set

The Enrolled Set will include all subjects enrolled from Cohort #2 and #3. Screen failures are not part of this set. Subjects with either 'Did the Eligibility Committee approve the subject for Implant?' = 'No' (Form: 'Informed Consent') or 'Is subject eligible to participate in this study?' = 'No' (Form 'Eligibility') will be considered as screen failure. For rescreened patients, the previous patient number will be considered as screen failure, and the rescreened patient number will be included in enrolled set. Unless specified otherwise, this set will be used for subject listings and summaries of subject disposition.

4.2. Intent-to-Treat Population

The Intent-to-Treat Population (ITT) will include all enrolled subjects intended to receive the Cordella PA Sensor who entered the Cath Lab, including those in whom Implant Procedure is not attempted for whatever reason (e.g. Cordella PA Sensor Implant cannot be performed due to anatomical reasons) from Cohort #2 and #3. Subjects in this population in whom the Cordella PA Sensor Implant is not attempted will be followed through 30 days for safety purposes. The ITT will be used for all analyses of safety endpoints. Efficacy analysis will not be performed on the ITT population.

4.3. Modified Intent-to-Treat Population (mITT)

The Modified Intent-to-Treat Population (mITT) will include all implanted subjects from Cohort #2 and Cohort #3. All primary and secondary efficacy analyses as well as primary safety analyses will be performed on the mITT.

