2. SIRONA 2: This CE-Mark study is ongoing in 8 European centers in Europe (Belgium, Ireland, Germany). SIRONA 2 is a prospective, multi-center, open-label, single-arm CE-Mark trial to assess device safety and efficacy of the Cordella PA Sensor System in up to 85 NYHA Class III HF patients who received the Cordella PA Sensor implant. Enrollment is finalized and the PA sensor was successfully implanted in 70 patients. The primary efficacy endpoint was the accuracy of PA sensor mean PAP measurements, compared with fluid-filled catheter mean PAP measurements obtained by standard RHC at 90 days post-implant, assessed in all patients with a successful implant. The primary safety endpoint was freedom from adverse events associated with use of the Cordella PA Sensor System through 30 days post-implant, assessed in all patients who entered the Cath Lab for a PA sensor implant. Equivalence between the PA sensor and RHC for mean PA pressures was within the equivalence bounds of - 4.0 to 4.0 mmHg (mean PAP: 0.0 to 2.9 mmHg, P = 0.003), therefore the primary efficacy endpoint was met. The device safety profile was excellent with 98.6% freedom from Device System Related Complications, defined as invasive treatment, device explant or death and with no pressure sensor failures. This study is ongoing and in long- term follow up, to date no safety or efficacy concerns have been reported.

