8.3.2 Study Visit 2 (Cordella PA Sensor Implant Visit: Admission & Implant)

Before the subjects return for the Cordella PA Sensor Implant Visit, they will be instructed by the Investigator to discontinue use of anticoagulation therapy 1-2 days prior to the procedure. The investigator should consider utilizing another anticoagulant per the site's standard-of-care as bridge therapy to Cordella PA Sensor placement in subjects who were on anticoagulation therapy.

Implant procedures for the Cordella PA Sensor are described in detail in section 6 of the IFU, which will be provided to each site at study start.

Implants may be performed via RHC using percutaneous venous access.

In case the Cordella PA Sensor Implant is attempted but not completed, subjects will be followed through 30 days for safety purposes.

It is critical that accountability of the device is maintained for research records. Federal regulations require that the lots / ID number of the device are appropriately noted and tracked (please also see Section 2.4).

The following study procedures will be performed during this visit:

- Cordella PA Sensor implant
- RHC PAP: diastolic, systolic, mean, HR, RAP, Pulmonary Capillary Wedge Pressure (PCWP), CO, Cardiac Index (CI), RVP: diastolic, systolic, end diastolic
- Cordella PA Sensor PAP: diastolic, systolic, mean, pulse (via CalEQ):
 - after calibration
 - seated and supine before discharge or at home (within 24 hours)
- Set Up/Subject Training: Cordella™ HF System (myCordella™ Tablet & Peripherals)
- Subject Training/Subject Use: CorPASS (myCordella™ Patient Reader and Dock)
- Abbreviated Physical Examination
- Concurrent/Cardiac Medications
- Adverse Event

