10.5 Safety Endpoints

There are two primary safety endpoints, Freedom from device/system related complication at 6 months and Freedom from pressure sensor failure at 6 months. Freedom from device or system related complications at 6 months will be tested against the null rate of 90%. Freedom from Pressure Sensor Failure at 6 months will be tested against the null rate of 95%.

Mathematical statements of the null and alternative hypothesis for each test are as follows:

$$H_0: S1 \leq PG_{S1}$$

$$H_A: S1 > PG_{S1}$$

and

$$H_O: S2 \leq PG_{S2}$$

$$H_A: S2 > PG_{S2}$$

where S1 and S2 represent the freedom-from-event rates for device/system related complication at 6 months, and pressure sensor failure at 6 months respectively, and PG_{S1} and PG_{S2} represent the corresponding performance goals with values expressed as a proportion of 0.90 and 0.95 respectively.

Each of these will be assessed within among all patients who underwent a device implant by estimating freedom from the event of interest at 6 months by the Kaplan-Meier method. The proportion event free at 6 months and the corresponding two-sided 95% confidence interval will be compared to the null rate. We use a one-sample test of binomial proportions with a two-sided Type I error rate of 5% to estimate the power available for these analyses.

A sample size of 450 patients provides greater than 95% power assuming a population rate of 95% for the freedom-from-event rates for device/system related complication at 6 months. Power would still be maintained at this level for an evaluable sample size of 406.

Similarly, a sample size of 450 patients provides approximately greater than 95% power assuming a population rate of approximately 98.4%, for the pressure sensor failure at 6 months endpoint. Power would still be maintained at this level for an evaluable sample size of 406.

Primary Safety Endpoints:

1. Freedom from device/system related complication at 6 months
2. Freedom from pressure sensor failure at 6 months

In addition to the two (2) primary safety endpoints with hypothesis tests, the following secondary safety endpoints will be summarized.

Secondary Safety Endpoints:

1. Pressure sensor failure rate throughout the study
2. Frequency of serious adverse events throughout the study
3. Frequency of implant procedure and procedure related adverse events and serious adverse events

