7.1.17. Functional status improvement measured by NYHA and 6-Minute Walk Test

NYHA functional classification: The subject's functional status is assessed by a qualified individual at the institution, who is not directly involved with this clinical trial, by utilizing the NYHA functional classification, described in the Protocol Appendix 14.2.

The NYHA functional classification categorizes the extent of heart failure by placing subjects in one of four (I, II, III, IV) categories based on how much they are limited during physical activity and symptoms of shortness of breath and/or angina.

This document is confidential.

NYHA functional classification will be obtained at all study visits as described in [Appendix 1: Time and Event Schedule](#) and must be NYHA Class III for study entry.

Shifts in NYHA functional classification from baseline over all post-baseline visits will be presented.

Six (6) Minute Walk: Subjects complete a six (6) minute walk test at the study visits described in [Appendix 1: Time and Event Schedule](#). Total distance walked (meters) will be collected and analyzed by means of descriptive statistics including the absolute value and change from baseline by visit.

Analysis will be done based on mITT population, PP population, and Cohort #1 population. Prior to the date of cut-off for the main analysis, it will be confirmed, if analysis based on PP population will be required.

This document is confidential.

8. Safety

The population used for safety analyses will be the ITT. Safety will be assessed on the basis of adverse events (AEs), clinical laboratory data, ECG parameters, Echocardiograms, physical examinations, and vital signs. Primary safety endpoint will be analyzed based on mITT. In addition, AEs will be analyzed based on Cohort #1 population. Primary safety endpoints will also be repeated on ITT, PP population and Cohort #1 population. Secondary safety endpoints will also be analyzed based on PP population and Cohort #1 population. For CEC related endpoints, tables and figures will be repeated using CEC adjudication results

Adverse events and other safety analyses will also be assessed. No formal statistical hypothesis tests will be conducted. Analyses will involve Kaplan-Meier curves for time to event outcomes, descriptive statistics (n, mean, standard deviation, median, minimum, and maximum) for quantitative outcomes, and count and frequency results for categorical outcomes.

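### The deciding test of freedom from device/system related complication (DSRC) is run on implanted subjects only, although both documents assign all safety endpoints to the ITT

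*SAP*

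**What the plan says.** **General rule.** SAP 4.2 states that "The ITT will be used for all analyses of safety endpoints"; Protocol 10.2.2 says the same. The ITT covers enrolled subjects intended for the sensor "who entered the Cath Lab, including those in whom Implant Procedure is not attempted for whatever reason".

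**Rule for the primary safety tests.** SAP 4.3 gives the definition "The Modified Intent-to-Treat Population (mITT) will include all implanted subjects from Cohort #2 and Cohort #3" and continues "All primary and secondary efficacy analyses as well as primary safety analyses will be performed on the mITT". SAP 8 repeats it: "Primary safety endpoint will be analyzed based on mITT". Protocol 10.5 has "Each of these will be assessed within among all patients who underwent a device implant", and Protocol 10.8 and SAP 5.3 and 8.1.1 agree. Protocol 10.2.3 gives the mITT an effectiveness role only, and SAP 10 does not list the population among its changes.

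**ITT repeat.** SAP 8 repeats both primary safety endpoints on the ITT (for DSRC, tables 14.3.1.1.4.2 and 14.3.1.1.16.2). No passage says what follows if the two populations disagree. The extreme-case and tipping-point tables are listed for the mITT only.

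**Follow-up without an implant.** Protocol 8.3.2: "In case the Cordella PA Sensor Implant is attempted but not completed, subjects will be followed through 30 days for safety purposes". Protocol 10.2.2 and SAP 4.2 attach the 30-day rule to a different group, those in whom no implant was attempted.

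**The concern.** Two populations are named for one confirmatory test, and for DSRC the choice is not neutral. Protocol 9.4 defines a DSRC as an event at least possibly related to the device or system that is treated invasively or leads to death or explant. No completed implant is required. The delivery system is one of the listed subsystems (Protocol synopsis, SAP 2.6). Appendix 14.6 words the system more narrowly, as sensor or external electronics, but the sensor is pre-mounted on the delivery catheter, so a failed attempt can still produce a DSRC.

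If such an event ends the attempt before the sensor is released, the subject is not implanted and leaves both numerator and denominator. Membership of the analysis set then depends partly on the outcome, and freedom from DSRC is biased upward whenever failed attempts carry more DSRCs than completed ones. The sponsor's own CE-mark study, described in Protocol 3.3, took its primary safety endpoint as "assessed in all patients who entered the Cath Lab for a PA sensor implant".

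Endpoint 2, sensor failure, is different: it needs an implanted sensor, so the mITT is the natural population there.

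**Working it through.** **Inputs.** Null 90%, planning rate 95%, 450 implanted, 406 evaluable, two-sided 5% binomial test (Protocol 10.5, SAP 2.4.3). The documents give no number of non-implanted subjects and no DSRC rate among them; both are assumed below. Exact binomial limits are used; the planned Kaplan-Meier interval may shift them slightly.

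**1. The plan's own figure.** The pass limit is the largest x with P(X ≤ x | n, 0.10) ≤ 0.025.
- n = 450: x = 32. The exact lower bound is 0.9011 at 32 events and 0.8986 at 33. The pass probability at the null is 0.021. Power at 95% is P(X ≤ 32 | 450, 0.05) = 98.1%.
- n = 406: x = 28, power 96.4%.

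The stated power above 95% reproduces, so the issue is the population and not the sample size.

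**2. How few events change the answer at the limit.** Suppose the mITT just passes with 32 of 450, and add m non-implanted subjects. The ITT fails once they contribute (ITT limit − 32 + 1) DSRCs.

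| m (assumed) | ITT size | ITT limit | DSRCs among m that flip the result |
|---|---|---|---|
| 5 | 455 | 32 | 1 |
| 9 | 459 | 33 | 2 |
| 14 | 464 | 33 | 2 |
| 23 | 473 | 34 | 3 |
| 45 | 495 | 36 | 5 |

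**3. Boundary illustration.** Let true freedom among all attempts be exactly 90%, with share f of attempts failing and share d of failures having a DSRC. The implanted risk is (0.10 − f·d)/(1 − f), and the mITT pass probability is P(X ≤ 32 | 450, that risk).

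| f | d = 0.3 | d = 0.5 |
|---|---|---|
| 2% | 0.040 | 0.071 |
| 3% | 0.054 | 0.122 |
| 5% | 0.097 | 0.305 |

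Without selection it is 0.021. If d equals the rate in completed implants, there is no bias.

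**4. At the rates the documents expect.** Protocol 1.3 cites DSRC below 2%, Protocol 3.3 reports 98.6% freedom in SIRONA 2, and the planning rate is 5%. Replace 0.10 by the overall rate, take 450·f/(1 − f) failures (9, 14 or 24), and sum over k DSRCs among them the probability that the implanted count is at most 32 but exceeds the ITT limit minus k.
- 5% among all attempts: the chance that the mITT passes and the ITT fails is at most 1.5% over the grid.
- 2% among all attempts: essentially zero. The corner f = 5%, d = 50% is impossible, since 0.05 × 0.5 = 2.5% already exceeds 2%.
- If 5% holds among implanted subjects only and failures come on top: 3% to 47%. At the upper end, freedom over all attempts is (450 × 0.95 + 24 × 0.5)/474 = 92.7%.

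**The case against.** The strongest reply is that the plan has in substance chosen. Every passage specific to the primary safety tests names implanted subjects, in both documents, and only one blanket sentence, carried in each, says otherwise. SAP 8 can be read as a general rule followed by an exception. That weakens the charge of confusion, but SAP 4.2 admits no exception, and the choice still conditions on a completed implant.

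A reader might infer that complications of failed attempts disappear from the trial. They do not. SAP version 2.1 added the ITT repeat, with investigator-reported and adjudicated tables and Kaplan-Meier plots, and the DSRC tables by term, severity and device are on the ITT. What is missing is a role in the decision.

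A reader might also count an embolised sensor, or a death after release, as lost from the mITT. The documents do not support this: the mITT is all implanted subjects, and a released sensor may well count as implanted. The clear loss is limited to complications before release.

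Nor do the 30-day passages show that complications go unfollowed. Protocol 9 requires adverse events to be followed to resolution or stabilisation. Complications of the attempt itself would mostly fall within 30 days, and Kaplan-Meier censoring keeps those.

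Finally, the ITT is not a perfect substitute. It includes subjects in whom nothing was attempted, and they dilute the DSRC rate in the device's favour.

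**Conclusion.** The concern holds in a limited form. Both documents contradict themselves on the population for the primary safety tests, and the version that governs lets a pre-release complication of a failed attempt fall outside the deciding DSRC test. The direction of the bias is clear if such attempts carry excess DSRCs; its size cannot be derived from the documents.

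Near the limit of 32 of 450, 1 to 5 events among an assumed 5 to 45 non-implanted subjects decide the outcome. It would be tempting to report a false-pass chance of up to about 30% as the expected effect. The documents do not support that: it requires true freedom of exactly 90% together with the highest assumed failure and DSRC shares. With 2% to 5% DSRC over all attempts, a change of conclusion is unlikely (at most 1.5% on the grid). The larger 3% to 47% arises only if failures add to a 5% rate among implanted subjects.

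This is a should-fix: one unambiguous population is needed for a test that supports the premarket submission, and the less biased one is already tabulated.

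**What to change.** 1. In SAP 4.3, 5.3, 8 and 8.1.1 and Protocol 10.5 and 10.8, name the ITT analysis (tables 14.3.1.1.4.2 and 14.3.1.1.16.2) as deciding for endpoint 1, freedom from DSRC. Keep the mITT as supporting for endpoint 1 and as primary for endpoint 2, sensor failure, and state that exception in SAP 4.2 and Protocol 10.2.2.
2. Add a sensitivity analysis of endpoint 1 restricted to subjects in whom an implant was attempted, to remove the dilution by subjects never attempted.
3. Reconcile the 30-day follow-up passages (Protocol 8.3.2 against Protocol 10.2.2 and SAP 4.2), and state that these subjects are censored at last contact in the ITT Kaplan-Meier analysis. SAP 8.1.1 already counts time from the implant visit, so no new time origin is needed.

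The cost is wording in both documents and one added table. Freedom from DSRC may look slightly less favourable.

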4.4. Per Protocol Population

The Per Protocol Population (PP) will include all mITT subjects without any major protocol deviations. All primary and secondary safety and efficacy analyses will be performed in addition on PP population. If PP and mITT populations will be identical, analysis will be performed based on mITT only.

4.5. Cohort #1 Population

This population will include all Cohort #1 (previously enrolled Control Arm) implanted subjects and will be reported separately for all applicable tables, figures and listings.

4.6. Comparison Population

This population will include all implanted subjects from Cohort #1, Cohort #2 and #3. The Comparison Population will be used for analysis of secondary efficacy endpoint #3.

